## Section 5: Trial Population

- 21: Screening data: We have not collected screening data but planned for a convenience sample of one year inclusion period.
- 22: Summary of eligibility criteria: All cesarean section category 1 in 2022 are eligible and mother and partners will be approached for consent to participate.
- 23: Information to be included in the CONSORT flow diagram: see template for Consort flow diagram for the trial.

24a: Level of withdrawal, eg, from intervention and/or from follow-up: We expect that 20% of the mothers and partners will decline to participate. We expect that >90% of partners, who accept to participate, will also participate in the follow-up interview.

24b: Timing of withdrawal/lost to follow-up data: NA

24c: Reasons and details of how withdrawal/lost to follow-up data will be presented: Data will be presented in the result section of the final manuscript.

25a and b: Baseline patient characteristics:

Table 1. Baseline data

	Kolding	Aabenraa
	n=	n=
Age of mother		
BMI, mother		
ASA score, mother		
Parity, mother		
Partner was present during		
cesarean section		
Age of partner		
Indication for cesarean section		
-fetal distress		
-bleeding		
-uterus rupture		
-other		
Time from calling the cesarean		
section till infant is delivered		
Bleeding, ml		
Need for blood transfusion		
APGAR scores		
-1 min		
-5 min		
-10 min		
Surgical complications		
-bladder perforation		
-bowel perforation		
-bleeding>1000 ml		
Anestesiological complications		
-difficult airway		
-esophageal intubation		
-aspiration		
Time from cesarean section to		
discharge from hospital		
Postoperative infection		
Need for repeat surgery		
Additional clinically relevant		
information from each cesarean		
section		

# Section 6: Analysis

#### 26: Outcome definitions

The primary outome will be the partners answer to the main study question: "Would you have preferred to wait outside the OR during the anesthesia and cesarean section?" for partners in Kolding and "Would you have preferred to be present in the OR during the anesthesia and cesarean section?" for partners in Aabenraa. This question is asked both at first interview (day 1 or 2 following the cesarean section) and at follow-up three months later. The number of partners answering "yes" will be shown in number and percentages, n (%).

Secondary outcomes will be narrative and tabular descriptions of questionnaire data from mothers, medical data regarding the cesarean section and infant, follow-up interviews and questionnaires from health care professionals.

27: Analysis methods: Descriptive statistics will be used where appropriate.

As cesarean section category 1 is usually performed by a smaller group of specialized clinicians, it is likely that the same clinicians will perform several of the cesarean sections in this study. As part of the analyses, data will be investigated for clinician-specific effects by including the clinician as a random effect in a mixed effect model and investigate the varians components. If there should be clinicial specific effects, against what we expect, the statistical analyses will include the found cluster structure and analyse as non-independent data.

28: Missing data: We will present the extent of missing data. No form of imputations for missing data will be used.

29: Additional analyses: None planned.

30: Harms: NA, as this is an observational study, describing the existing practice in two different hospitals.

31: Statistical software: STATA will be used.

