#### Section 2: Introduction

#### 7: Synopsis of trial background and rationale

This study concerns cesarean sections, category 1, meaning those cases where the life of mother and/or fetus is in immediate danger and the child must be delivered within 15 minutes from activating the cesarean section team. In most hospitals in Denmark, these cesarean sections are most often performed in general anesthesia and the mother is endotracheally intubated.

Previously in these situations, as the mother was rushed from the Labour Ward to the operation room (OR), her spouse/partner, would be placed outside the OR, and would stay there until the child had been delivered.

In Lillebaelt Hospital, Kolding, Denmark, the newborn-resuscitation table is placed inside the OR. The partner would most often be allowed to enter the OR when the child was delivered and placed on the resuscitation table (no matter the status of the child). However, during 2021, Lillebaelt Hospital Kolding updated the policy regarding the handling of the partner during cesarean section category 1 (implemented in the local guideline December 2021). Now the partner is present in the OR during the whole procedure, including the induction of general anesthesia, endotracheal intubation, performing the cesarean section (drapings are positioned so that the partner cannot see the operation field) and potential resuscitation efforts of the newborn.

In another hospital in the same region (Region of Southern Denmark), Aabenraa Hospital, the partner is not present in the OR during the cesarean section category 1. The partner waits in the labour ward.

The investigators therefore wish to investigate how the cesarean section category 1 is experienced by: the partner; the mother; the obstetrician; the anesthesiologist; the midwife; the OR nurse; the anesthetic nurse, both in Kolding where the partner is present in the OR, and in Aabenraa, where the partner is not present in the OR during the cesarean sectio.

In 2020 there were 16 cesarean sections category 1 in Kolding and 15 in Aabenraa.

8: Description of specific objectives or hypotheses

We hypothesize the mothers and partners will prefer the partner being present in the OR during the cesarean section category 1.

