#### Sectio 3: Study methods

- 9: Trial design: This is prospective cohort trial with two parallel cohorts in two centers (Kolding and Aabenraa).
- 10: Randomization: This is a non-randomized trial.
- 11: Sample size: The trial is based on a convenience sample consisting of all the cesarean sections in 2022 in each of the two participating centers.
- 12: Framework: This is an exploratory trial without statistical power to perform superiority, equivalence, or noninferiority hypothesis testing.
- 13: Statistical interim analyses: NA

14: Timing of final analysis: All analyses will be conducted when the inclusion period has ended (January 1st 2023).

15: Timing of outcome assessments: outcomes will be assessed for each cesarean section (first questionnaire in day 1 or 2 following the cesarean section, follow-up interview three months later). Data on outcomes will be analyzed when the inclusion period has ended.

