### Section 4: Statistical Principles

16: Level of statistical significance: a p-value of <0.05 will be considered significant. However, due to the expected low number of cases (expected approx. 15 cesarean section category 1/year in each center), it is likely that descriptive statistics will be most appropriate.

- 17: Description and rationale for any adjustment for multiplicity: NA
- 18: Confidence intervals to be reported: see 16.

19a: Definition of adherence to the intervention: for each cesarean section is will be described whether or not the partner was present in the operation room during the cesarean section.

19b: Description of how adherence to the intervention will be presented: the information will be available in the result section in the final manuscript.

19c: Definition of protocol deviations for the trial: for various reasons the partner may or may not be present in the OR even though he/she was supposed to or supposed not to; there might not be a partner, the partner could be ill or otherwise occupied etc.

19d: Description of which protocol deviations will be summarized: in tabular form in the result section in the final manuscript.

20: Definition of analysis populations, eg, intention to treat, per protocol, complete case, safety: We will perform intention-to-treat analyses. However, as the trial aims to explore the situation of having the partner present in the OR versus not having the partner present, we will also assess data per protocol, if it turns out that there are multiple cases of protocol deviations. This will be done using descriptive statistics, and without statistical tests.

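### Does reporting only the share of *yes* answers spoil the primary outcome, given that the two hospitals ask opposite questions?

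*SAP*

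**What the plan says.** Item 26 fixes the primary outcome as the partner's answer to one question, worded by hospital. Kolding partners, who are normally in the OR, are asked "Would you have preferred to wait outside the OR during the anesthesia and cesarean section"; Aabenraa partners, who normally are not, are asked "Would you have preferred to be present in the OR during the anesthesia and cesarean section". The question is put on day 1 or 2 and again at three months. The summary is "The number of partners answering 'yes' will be shown in number and percentages, n" (%).

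Item 8 gives the expected direction: "We hypothesize the mothers and partners will prefer the partner being present in the OR during the cesarean section category 1". Item 9 describes "two parallel cohorts in two centers (Kolding and Aabenraa"), and item 12 calls the trial exploratory, without power for hypothesis testing.

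Item 19c accepts that "the partner may or may not be present in the OR even though he/she was supposed to or supposed not to". Item 19d tabulates such deviations. Item 20 makes intention-to-treat the main analysis and then, because "the trial aims to explore the situation of having the partner present in the OR versus not having the partner present", adds: "we will also assess data per protocol, if it turns out that there are multiple cases of protocol deviations". That second look is descriptive and without tests.

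**The concern.** A reader who sees two *yes* percentages side by side expects them to measure the same thing, and here they do not. If item 8 is right, *yes* should be low in Kolding and high in Aabenraa, and the plan never says so. The answer that supports the hypothesis in Kolding is *no*, which item 26 does not promise to show. If the raw *yes* counts were compared or added across centres, identical preferences would look like a large difference between hospitals.

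The per-protocol look raises a second worry. Question wording follows the hospital, not what happened to the partner. If item 20 means sorting partners by actual presence, a group could hold answers to both questions, and its *yes* percentage would mix two opposite meanings. With so few partners, one misplaced answer is visible.

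**Working it through.** **Inputs.** About 15 category 1 sections per centre per year (item 16) and 20% of partners declining (item 24a). Assumptions, because the SAP gives no figures: the same share *p* prefers presence in both centres; everyone answers yes or no; *d* partners deviate from local practice, with *d* from 0 to 3. The SAP has no sample-size or power figure to reproduce (item 11, convenience sample).

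**Partners per centre.** 15 × (1 − 0.20) = 12, so one partner is 1/12 = 8.3 percentage points.

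**Planned display, by centre.** Kolding *yes* = 12(1 − p); Aabenraa *yes* = 12p.

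| p | Kolding *yes* | Aabenraa *yes* |
|---|---|---|
| 0.5 | 6.0 of 12 (50%) | 6.0 of 12 (50%) |
| 0.7 | 3.6 of 12 (30%) | 8.4 of 12 (70%) |
| 0.9 | 1.2 of 12 (10%) | 10.8 of 12 (90%) |

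Each figure correctly answers the question asked in that centre, and the pattern is the one item 8 predicts.

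**A comparison that item 26 does not plan.** If 10 of 12 prefer presence in both centres, raw *yes* is 2/12 (17%) against 10/12 (83%), with Fisher's exact p = 0.003. Recoded to preference for presence, both centres show 10/12. The misreading would be serious, but it requires a step that the plan does not contain.

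**Per-protocol look, deviating partners excluded.** The present group holds only Kolding partners and the not-present group only Aabenraa partners. Expected *yes* stays at 1 − p and p: 10% and 90% at p = 0.9, for any *d*.

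**Per-protocol look, partners regrouped, *d* deviations in each centre.** Present = [(12 − d)(1 − p) + dp]/12; not present = [(12 − d)p + d(1 − p)]/12. The shift towards 50% is (d/12)|2p − 1|.

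| d per centre | p = 0.9, present / not present | p = 0.7, present / not present |
|---|---|---|
| 0 | 10% / 90% | 30% / 70% |
| 1 | 16.7% / 83.3% | 33.3% / 66.7% |
| 2 | 23.3% / 76.7% | 36.7% / 63.3% |
| 3 | 30% / 70% | 40% / 60% |

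At p = 0.5 nothing moves.

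**Partners regrouped, deviations in Kolding only.** The examples in item 19c (no partner, partner ill or otherwise occupied) all produce absence, which departs from local practice only in Kolding. The present group then stays at 1 − p, which is 10% at p = 0.9. The not-present group is [12p + d(1 − p)]/(12 + d). At p = 0.9:

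- d = 1: 10.9/13 = 83.8%
- d = 2: 11.0/14 = 78.6%
- d = 3: 11.1/15 = 74.0%

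A case with no partner yields no answer and moves nothing.

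**What a recode would cost.** Treating a Kolding *no* as equal to an Aabenraa *yes* is not neutral. An indifferent partner who answers *no* counts for presence in Kolding and against it in Aabenraa. With *k* such partners per centre the artificial gap is k/12: 8.3, 16.7 and 25.0 points for k = 1, 2 and 3.

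**The case for a change.** The strongest case for a change is that this is the only primary outcome and that a few lines would settle it before data are seen. Item 20 justifies its second look by actual presence, which points towards regrouping, while its label points towards exclusion; the choice is left open. Item 26 also does not list the answer categories, so if some partners are undecided, *no* cannot be found by subtracting *yes* from the total. And the clinician mixed model in item 27 names no outcome, so a model of the raw answer over both centres is not expressly ruled out.

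Part of this stands. Item 20 does leave open exclusion or regrouping, and does not say how many deviations count as multiple. But the look is conditional, descriptive and secondary, and deviating partners are already handled by the intention-to-treat analysis, the deviation table in item 19d and the actual-presence row in Table 1. Per protocol ordinarily means exclusion; sorting by exposure received is usually called as-treated. The answer categories belong to the questionnaire, which is not at hand; if the answer is yes or no, *no* follows from the count and the extent of missing data promised in item 28. Anyone modelling the answer across centres must first decide what the response variable is, and the two questions stand next to each other in item 26.

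**Conclusion.** No change to the plan follows. The direction of *yes* does reverse between centres, but the meaning is plain from the questions, each of which asks whether the partner would have preferred the alternative to local practice. That is a coherent descriptive outcome for each hospital, and a column label in the results table is enough to present it. A common recode would bring its own asymmetry of 8.3 points per indifferent partner, so it is no clear gain for the planned by-centre display.

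The remaining gap is the unstated per-protocol rule in item 20. Under exclusion its effect on the expected *yes* figures is nil. Under regrouping, at p = 0.9 with one to three deviations in Kolding only, it lowers the not-present figure from 90% to between 83.8% and 74.0% and leaves the present figure at 10%. Equal deviations in both centres would move both groups, at most to 30% and 70% over the range shown. These sizes rest on 12 answering partners per centre, equal preference in both hospitals and assumed values of *d*. This is missing detail in a secondary display, which an analyst can settle sensibly, and not an error in the primary outcome.

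### Item 27 allows for repeated clinicians only if a mixed model on about 24 to 30 sections finds a clinician effect, a test-then-decide rule that is unreliable at this size

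*SAP*

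**What the plan says.** SAP section 6, item 27, states that "it is likely that the same clinicians will perform several of the cesarean sections in this study". It then plans to check for clinician effects by "including the clinician as a random effect in a mixed effect model and investigate the varians components". What follows is conditional: "If there should be clinicial specific effects, against what we expect, the statistical analyses will include the found cluster structure". No criterion for an effect having been found is given, and no outcome is named for the model.

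The item speaks of the clinician in the singular. Section 2, item 7, lists five staff roles whose experience is studied: "the obstetrician; the anesthesiologist; the midwife; the OR nurse; the anesthetic nurse".

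The rest of the SAP is mostly descriptive:

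- Item 12 calls the study an "exploratory trial without statistical power to perform superiority, equivalence, or noninferiority hypothesis testing".
- Item 16 sets a threshold, "a p-value of <0.05 will be considered significant", but considers description the likelier outcome because of the low numbers ("expected approx. 15 cesarean section category 1/year in each center").
- Item 18 reads "Confidence intervals to be reported: see 16".
- Item 26 presents the primary outcome as n (%) and the secondary outcomes, including the staff questionnaires, as narrative and tables.

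**The concern.** The plan foresees that one person will contribute to several sections, so dependence is built into the staff and section-level data. Whether the analysis respects it is then decided by a look at the same small data set. A variance component estimated from a handful of clinicians is very imprecise. A moderate effect will often go undetected, and the analysis then proceeds as if the observations were independent.

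At stake are standard errors that are too small for any interval or p-value on staff answers or section-level data. There is also a possible statement in the paper that no clinician effect was found, which readers could take as evidence of independence.

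**Working it through.** **Inputs from the SAP.** About 15 sections per centre (item 16), so about 30 in all. Item 24a expects 20% of mothers and partners to decline, and 30 × 0.8 = 24. No staff response rate is given, so 24 is used only as a lower figure. The SAP contains no power or error-rate figure to reproduce.

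**Assumptions, none in the SAP.** Continuous score, one staff role, clinicians nested in centre, balanced data, ICC (ρ) from 0 to 0.3. Three designs, as clinicians per centre × sections each: 4×3 (24 sections), 5×3 (30) and 6×2 (24).

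**Chance that a 5% test finds the effect.** With K clinicians in total and m sections each, the F test has K − 2 and K(m − 1) degrees of freedom, and

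P(found) = P(F > Fcrit / [1 + mρ/(1 − ρ)]).

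At ρ = 0.2, ρ/(1 − ρ) = 0.25:

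- 4×3: df 6 and 16, Fcrit 2.741; 2.741/1.75 = 1.57; P = 0.22.
- 5×3: df 8 and 20, Fcrit 2.447; 2.447/1.75 = 1.40; P = 0.26.
- 6×2: df 10 and 12, Fcrit 2.753; 2.753/1.50 = 1.84; P = 0.16.

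**Consequence for a two-centre comparison.** In simulation (40,000 studies per setting), an ordinary t test is used if nothing is found. If an effect is found, a t test on clinician means with K − 2 degrees of freedom is used. Nominal error is 5%.

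| Design | Found, ρ 0.2 / 0.3 | Type I error, ρ 0.2 / 0.3 |
|---|---|---|
| 4×3 | 22% / 36% | 8.1% / 9.4% |
| 5×3 | 26% / 42% | 8.2% / 8.4% |
| 6×2 | 16% / 26% | 6.6% / 7.3% |

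Repeat runs agree to within about 0.3 percentage points. Coverage of a 95% interval for a centre mean is 92–94% at ρ = 0.2 and 91–93% at ρ = 0.3. At smaller effects the excess is small: type I error is 5.2–5.6% at ρ = 0.05 and 5.7–6.8% at ρ = 0.1. If clinician means are always used, the error is about 5% in every setting.

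**The other natural criterion: any positive variance estimate.** This flags 46–49% of studies with no clinician effect at all, and 73–89% at ρ = 0.2–0.3. Type I error is 3.1–4.9% over ρ = 0–0.3, provided the flagged analysis uses small-sample degrees of freedom. With a 1.96 reference after flagging it is about 6–8% at ρ = 0.2–0.3.

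**Sensitivity to the assumed designs.** With 15 sections per centre spread unevenly over 8 to 10 clinicians, the 5% test finds the effect in 12–27% of studies at ρ = 0.2–0.3, and the error is 6.3–7.7%. With fewer clinicians it is worse: 2 per centre with 6 sections each gives 9.7%, 13.8% and 15.7% at ρ = 0.1, 0.2 and 0.3.

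**The case against.** The strongest reply is that the SAP names no analysis to which these error rates apply. Every outcome in item 26 is a count with a percentage, a table or a narrative; item 12 disclaims power for testing; and no two-centre test or centre-mean interval is specified. This largely stands and sets the reach of the point. It does not remove it: item 16 keeps a significance threshold, item 18 defers to item 16, and item 27 itself plans a model and further statistical analyses.

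A second reply is that looking at variance components is not a 5% test, and item 16 does not link its threshold to them. That is correct, which is why the positive-estimate reading is shown as well. A reader might infer that this reading is safe, or that the choice of criterion alone decides the result. Neither follows. The favourable error rates depend on small-sample degrees of freedom after flagging, and item 27 specifies no such step.

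A reader might also infer that the primary outcome is compromised. The documents do not support this: it is one partner's answer per section at each time point, shown as n (%), and that description does not rest on independence.

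Finally, the missing threshold and the undefined role could be read as faults in themselves. On their own they are only missing detail, and the reference to those who perform the sections narrows the role somewhat without settling it. The point is that the rule is conditional.

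**Conclusion.** The point holds within narrow limits and is a matter to consider, not a threat to the study's main result. Making the allowance for clustering depend on a variance-component check is unreliable with about 24 to 30 sections. Under the three balanced designs and a 5% test, a real effect at ICC 0.2 to 0.3 is missed in roughly 58 to 84% of studies (100 − 42 and 100 − 16), and the two-centre error is about 7 to 9%.

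These sizes rest on assumed clinician numbers, ICCs and a continuous score. They do not carry over to pooling all five roles or directly to yes/no answers. That a failure to find an effect in so few sections is not evidence of independence holds across all the designs examined. Only intervals or p-values on staff answers or section-level data are exposed, and only if any are produced.

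**What to change.** Replace the conditional step in item 27 with a few sentences:

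- Keep the item 26 outcomes descriptive, and report the number of distinct clinicians and the number of answers by role.
- For any interval or p-value on staff or section-level data, name the role that defines the cluster and allow for it whatever the variance estimate shows.
- Use a small-sample method. For continuous scores, use clinician means, or keep the random effect with small-sample degrees of freedom. Leave binary or ordinal answers descriptive, or use a cluster method suited to them.
- Do not report the absence of a detected clinician effect as evidence of independence.

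The cost is wider intervals. For a centre mean with 4 to 6 clinicians per centre, always keeping the random effect gives intervals about 1.05 to 1.13 times the naive width when there is no clinician effect, and 1.13 to 1.42 times at ICC 0.2 to 0.3. Clinician means give about 1.1 to 1.4 times and 1.3 to 1.8 times. In the balanced designs, always keeping the random effect held type I error at 3.2 to 5.0% over ICC 0 to 0.3. It was not tested in the unbalanced ones.
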